2.3 Secondary Endpoints

- A weight loss percentage at 10 weeks, 16 weeks and at end of trial (= 52 weeks from start)
- A proportion of patients with a weight loss percentage of 5% or more at 10, 16, 26 and 52 weeks
- A proportion of patients with a weight loss percentage of 10% or more at 10, 16, 26 and 52 weeks
- The time to reach a weight loss percentage of 5% and 10%
- The dose of naltrexone/bupropion used at 10, 16, 26 and 52 weeks and at the end of the trial
- The tolerability of VLCKD and NB
- Adherence to VLCKD and NB
- The Patient-Reported Outcome Measures (PROMs) of hunger and cravings at 0, 4, 10, 16, 26 and 52 weeks
- The change in fasting glucose, lipids and blood pressure at 10, 16, 26 and 52 weeks]

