5.1.5 Pharmacovigilance

Any adverse reactions related to the medicinal products used by the participants in the study, can be reported to the Marketing Authorisation Holder and/or the Competent Authorities according to the pharmacovigilance guidelines.

6 Statistics and Data Analysis

Statistical analysis will be performed in accordance with ICH E9; a detailed description of the analysis is provided in the Trial-specific Statistical Analysis Plan (SAP). ICH E3 and E8 will guide the structure and content of the clinical trial report.

[The hypothesis for this trial is that the percentage of weight loss will be greater for the experimental arm than the comparator arm.]

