6.1 Sample Size Determination

The sample size was determined for a two-sided two-sample t-test to test the difference in mean weight loss percentage between both treatment arms, assuming a mean weight loss of 6.75% (SD 7.12%) [unpublished, own retrospective data] in the control arm and a mean weight loss of 12% (SD 5.3) [unpublished, data provided by Pro Well] in the intervention arm. Assuming a 20% drop-out rate, a 5% significance level and 80% of power, a total sample size of 62 patients is indicated, or 31 patients per study arm

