6.2 Statistical Analysis

[The primary analysis will be performed using a two-sample two-sided t-test to test the difference in mean weight loss percentage between both treatment arms. Mean weight loss percentages and the mean difference in weight loss percentage will be estimated and presented with 95% confidence intervals. A 5% significance level will be adopted for the primary analysis. Given the pragmatic nature of the trial, the primary analysis will be performed following the intention-to-treat (ITT) principle, in that all randomized patients will be analyzed in the study arm in which they were randomized, regardless of adherence to the therapy assigned to the patient. In presence of missing outcome data due to drop-out of patients for whom

no follow-up data were collected, the method of multiple imputation will be used. Fully conditional specification will be used to create 10 complete data sets, of which each will be analyzed and analysis results combined according to multiple imputation principles. Treatment arm and previous weight loss measures will be used as predictors in the imputation model.

A per protocol (PP) analysis will be performed as a secondary analysis, including patients adherent to the randomized treatment. Missing data will be dealt with as described above, using multiple imputation.

Linear mixed models for longitudinal data will be used for the analysis of a treatment effect on weight loss percentage at other time points. The explanatory model will contain treatment arm, time point and the interaction thereof. A random effect for patient will be modelled to deal with data clustering. Results will be presented as mean differences per time point with 95% confidence intervals.

The treatment effect on the proportion of patients with weight loss at various time points will be analyzed using logistic regression analysis, with generalized estimating equations (GEE) to account for data clustering. The explanatory model will contain treatment arm, time point and the interaction thereof. Results will be presented as odds ratios per time point with 95% confidence intervals

The treatment effect on the time to reach a pre-defined weight loss percentage will be analyzed using a log-rank test for time-to-event outcomes. Additionally, a Cox model will be used for the estimation of the hazard ratio with 95% confidence interval.

Descriptive analyses will be used for tolerability or adherence to treatment.]

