6.2.1 Efficacy Analysis

Endpoint	Statistical Analysis Methods
Primary	Two-sided two sample t-test, with analysis following the intention-to-treat principle and multiple imputation to deal with missing data.
Secondary (if applicable)	Linear mixed models for continuous and longitudinal data. Logistic regression for binary and longitudinal data. Log-rank test and Cox model for time-to-event data. Descriptive statistics for adherence and tolerability.

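### The mixed model for secondary weight loss names only a patient random effect; read as a random intercept with constant residual variance, its per-visit 95% intervals are mis-sized if the SD differs between visits (low severity)

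*Protocol*

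**What the plan says.** Section 6.2 of the protocol gives the method for the non-primary visits: "Linear mixed models for longitudinal data will be used for the analysis of a treatment effect on weight loss percentage at other time points". The fixed effects are arm, time point and their interaction. Within-patient dependence is handled in one sentence: "A random effect for patient will be modelled to deal with data clustering". The output is also fixed: "Results will be presented as mean differences per time point with 95% confidence intervals". The table in section 6.2.1 repeats the method as "Linear mixed models for continuous and longitudinal data" and adds no covariance structure.

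The opening of section 6 refers to a further document: "a detailed description of the analysis is provided in the Trial-specific Statistical Analysis Plan (SAP"). That document is not at hand.

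Section 6.1 gives one SD per arm, with no week attached: "assuming a mean weight loss of 6.75% (SD 7.12"%) in the control arm and 5.3 in the intervention arm. For the primary week-26 endpoint, section 6.2 says: "The primary analysis will be performed using a two-sample two-sided t-test". The Study Flowchart has weight measured at V2, but neither the t-test nor the listed predictors of the imputation model include baseline weight.

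**The concern.** A random intercept with constant residual variance gives every visit the same total variance. The standard error of each arm difference then rests on the average variance over visits and not on that visit's own.

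There is reason to doubt a constant SD. The outcome is change relative to baseline (section 2.2), so its spread is zero at the start and must grow at first. The visits also fall in different phases: diet in one arm up to week 10, common treatment up to week 26, then follow-up to week 52 (section 2.4). How far the SD still moves between weeks 10 and 52 cannot be known from the protocol.

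At stake are the intervals reported for a listed secondary endpoint, weight loss at weeks 10, 16 and 52. One that covers 85% or 92% overstates precision at that visit; one that covers 99% understates it. The stake is limited, since each of these visits is also described by responder proportions, for example "A proportion of patients with a weight loss percentage of 5% or more at 10, 16, 26 and 52 weeks".

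**Working it through.** **The plan's own figure.** Inputs from section 6.1: means 6.75 and 12, SDs 7.12 and 5.3, two-sided 5%, power 80%, drop-out 20%. Difference 12 − 6.75 = 5.25. Root mean square SD = √((7.12² + 5.3²)/2) = 6.276. A t-test needs 24 per arm (power 0.81), and 24/0.8 = 30 per arm, 60 in total. Taking 25 per arm gives 50/0.8 = 62.5. The stated 62 is reproduced to within two patients, and it does not depend on the mixed model.

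**Formula for the secondary model.** With complete data, n per arm and arm-by-visit effects:
- model-based variance of each visit's arm difference = (2/n) × mean of the four visit variances;
- true variance = (2/n) × that visit's own variance;
- with k = visit SD / root mean square SD, coverage = 2Φ(1.98/k) − 1.

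So k = 1.05, 1.10 and 1.20 give 94.1, 92.8 and 90.1%. Only the ratio of SDs between visits matters, not their level.

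**Numbers.** All visit SDs are assumptions, linear over the four visits. Week 26 is taken to be in the model, which the protocol does not say. Example for 4 to 8: SDs 4, 5.33, 6.67, 8; root mean square 6.18; at week 52, k = 8/6.18 = 1.294 and coverage = 2Φ(1.53) − 1 = 87.4%.

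| SD, week 10 to week 52 | Formula: coverage (%) at weeks 10, 16, 26, 52 | Simulation with dropout (%) |
|---|---|---|
| flat | 95, 95, 95, 95 | 95, 95, 95, 95 |
| 5.7 to 6.9 | 97, 96, 95, 93 | 97, 95, 94, 92 |
| 5 to 7.5 | 99, 97, 94, 90.5 | 99, 96, 93, 88 |
| 4 to 8 | 99.8, 98, 93, 87 | 99.6, 97, 92, 85 |
| 7.5 to 5 (falling) | 90.5, 94, 97, 99 | 91, 94, 97.5, 99 |

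Simulation: 2,000 trials per case, 31 per arm with two per arm lost at random at each of weeks 16, 26 and 52 (25 left), correlation decaying from 0.85, REML with Kenward-Roger standard errors. Simulation error is about 0.5 points near 95% and 0.8 near 85%. In the 4-to-8 case the model's standard errors were 1.52-1.60 against true values of 1.00, 1.37, 1.74 and 2.16. An equal correlation of 0.6 changed little: week-52 coverage was 92.4% (5.7 to 6.9) and 85.3% (4 to 8).

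**Alternatives in the same simulations.**
- Random intercept with four visit-specific residual variances: for the three rising cases, week-52 coverage 94.8, 93.4 and 91.8%, week-10 coverage 96.8, 98.4 and 99.2%. The error shrinks but remains.
- Unstructured covariance with Kenward-Roger: 94.5-95.2% at every visit in all five cases under the decaying correlation, and 94.5-96.5% under the equal correlation.
- Price when the SDs are equal: unstructured intervals 0.1-1.9% wider.
- Mean error of the point estimates: at most 0.06 percentage points under any model.

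**Optional baseline adjustment at week 26.** With r the correlation between outcome and baseline weight, ANCOVA multiplies both SDs by √(1 − r²) and costs one degree of freedom. At 25 per arm, unadjusted, the noncentrality is 5.25/√((7.12² + 5.3²)/25) = 2.957 with Welch df 44.3, giving power 82.5%. For r = 0, 0.1, 0.2, 0.3 and 0.4, ANCOVA gives 82.4, 82.8, 83.9, 85.8 and 88.4%.

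**The case against.** The strongest reply is that covariance structure, degrees of freedom and convergence fallbacks are normal SAP content, and section 6 defers detail to an SAP. That limits the request but does not dispose of it. The sentence is not silent on clustering: it picks a device and gives its purpose. An SAP that followed it literally would inherit the problem, and one with another structure would leave the protocol sentence out of line.

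Second, the protocol never says that residual variance is constant. This stands. The wording leaves room for visit-specific residual variances, which reduce the error, and also for a random slope, serially correlated residuals or robust standard errors, none of which was simulated.

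Third, nothing in the protocol shows that SDs differ by visit, and the 85% figure needs the SD to double between weeks 10 and 52. This also stands; the figure marks one end of an assumed range.

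A reader might infer that the protocol commits to a wrong model, or that the week-52 interval will cover only 85%. The documents support neither: both conditions are assumptions, and with a falling SD the week-52 interval would be too wide. A reader might also take the unadjusted t-test for a mistake. It is valid and matches the method used for the sample size.

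**Conclusion.** The point holds as a cheap improvement of low severity, not as a proven error. It rests on two conditions that the protocol does not establish: that the patient random effect is fitted as a random intercept with constant residual variance, and that the SD of percentage weight loss differs between visits. If both hold, intervals are too wide at visits with below-average SD and too narrow at visits with above-average SD. Combining formula and simulation, week-52 coverage is about 92-93% for a mild rise (5.7 to 6.9) and about 85-87% for a doubling (4 to 8). If the SD is flat there is no error. The effect is confined to the widths of secondary intervals.

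Use of baseline weight at week 26 is a separate, optional gain in efficiency. It is probably small, because the endpoint is already divided by baseline weight, so a low correlation is plausible.

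**What to change.** In section 6.2, replace the patient random effect for this analysis by an unstructured within-patient covariance over weeks 10, 16, 26 and 52, with Kenward-Roger degrees of freedom. Name a fallback that keeps separate variances by visit if the fit fails, for example heterogeneous compound symmetry or heterogeneous AR(1). If the SAP already fixes such a structure, make the protocol sentence agree with it. Do this before outcome data are seen, so that the structure is not chosen after the fact.

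Cost: wording only, no new data. If the SDs are in fact equal, intervals are about 0.1-3% wider (0.1-1.9% in the simulations, with some allowance). Four visits mean 4 × 5/2 = 10 covariance parameters from roughly 50-62 patients, which may not always converge; the fallback covers that, and all 16,000 simulated unstructured fits gave usable estimates.

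Optional: compare week-26 percentage weight loss by ANCOVA on arm and baseline weight within the same multiple imputation, and add baseline weight to the imputation model. The weight is already collected at V2. The cost is one degree of freedom: power 82.5% becomes 82.4% if baseline weight is unrelated to the outcome.

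### Section 6.2 gives the 5% and 10% responder GEE no missing-data method; run on available weights, it needs a stronger drop-out assumption than the primary analysis

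*Protocol*

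**What the plan says.** Protocol section 2.3 lists two responder endpoints: "A proportion of patients with a weight loss percentage of 5% or more at 10, 16, 26 and 52 weeks" and "A proportion of patients with a weight loss percentage of 10% or more at 10, 16, 26 and 52 weeks".

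Section 6.2 says that these proportions will be compared by logistic regression "with generalized estimating equations (GEE) to account for data clustering", with arm, time point and their interaction in the model. The output is also fixed: "Results will be presented as odds ratios per time point with 95% confidence intervals". The paragraph names no analysis set and no handling of missing weights.

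Missing data are dealt with elsewhere in section 6.2. In the primary-analysis paragraph, for drop-outs for whom "no follow-up data were collected, the method of multiple imputation will be used", there are ten data sets by fully conditional specification, and "Treatment arm and previous weight loss measures will be used as predictors in the imputation model". The per-protocol paragraph then says that the same approach applies there. The table in section 6.2.1 follows the same pattern: imputation appears in the primary row, while the secondary entry reads only "Logistic regression for binary and longitudinal data".

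Section 6 refers the reader to a separate SAP, not available here, for the detailed description.

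**The concern.** Three analyses in section 6.2 use the same visit weights: the imputed t-test at week 26, the linear mixed model at the other visits, and the responder GEE. The imputation conditions on arm and earlier weight loss, and the mixed model uses each patient's earlier measurements through the likelihood. Both can therefore tolerate drop-out that depends on weight loss already observed. Unweighted GEE on available data generally cannot. It needs drop-out to be completely random given what is in the model, here arm and time point.

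In a weight-loss trial, patients who lose little early on may well be the ones who leave. The protocol itself allows for 20% drop-out (section 6.1). In that situation the responder proportions among patients still attending would be too high. The week-26 responder result and the week-26 mean difference would also rest on different patients and different assumptions, although both come from the same weight.

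**Working it through.** **Inputs from the protocol (section 6.1).** Comparator mean loss 6.75%, SD 7.12%; diet arm 12%, SD 5.3; two-sided 5% level, 80% power, 20% drop-out, 31 per arm.

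**The plan's own figure.** Root-mean-square SD = √[(7.12² + 5.3²)/2] = 6.28; difference = 12 − 6.75 = 5.25. A two-sided t-test has 79.2% power with 23 per arm and 81.0% with 24. 24/0.8 = 30 per arm, or 60 in total, within two patients of the stated 62. Conversely, 31 × 0.8 = 24.8, so about 25 completers per arm.

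**Responder rates implied by those inputs, assuming normality.** P(loss ≥ c) = 1 − Φ((c − mean)/SD).

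- ≥5%, comparator: 1 − Φ(−0.246) = 59.7%; diet: 1 − Φ(−1.321) = 90.7%.
- ≥10%, comparator: 1 − Φ(0.456) = 32.4%; diet: 1 − Φ(−0.377) = 64.7%.
- Odds ratios: (0.907/0.093)/(0.597/0.403) ≈ 6.6 for ≥5%; about 3.8 for ≥10%.

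**Effect of drop-out (assumed; not in the protocol).** One million simulated patients per arm, with correlation 0.8 between earlier and week-26 loss. In scenario A, 20% leave in each arm, with log-odds of leaving rising by 1 per SD of poorer earlier loss. In scenario B, drop-out depends on earlier loss being below 5% in absolute terms, giving 21.6% (comparator) and 14.2% (diet). The available-weights column corresponds to GEE with an independence working correlation.

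| Scenario | Threshold | Arm | All patients | Available weights | Imputed from earlier loss |
|---|---|---|---|---|---|
| A | ≥5% | Comparator | 59.7% | 65.4% | 59.7% |
| A | ≥5% | Diet | 90.7% | 93.6% | 90.7% |
| A | ≥10% | Comparator | 32.4% | 36.9% | 32.4% |
| A | ≥10% | Diet | 64.7% | 70.3% | 64.7% |
| B | ≥5% | Comparator | 59.7% | 64.0% | 59.7% |
| B | ≥5% | Diet | 90.7% | 91.9% | 90.7% |
| B | ≥10% | Comparator | 32.4% | 35.8% | 32.4% |
| B | ≥10% | Diet | 64.7% | 66.2% | 64.7% |

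- Over correlations 0.6 to 0.9 and both scenarios, the excess runs from 0.8 to 6.4 points.
- Completely random drop-out gives no excess.
- The odds ratio has no fixed direction. In A it rises from 6.54 to 7.72 (≥5%) and from 3.82 to 4.04 (≥10%). In B it falls from 6.55 to 6.36 and from 3.82 to 3.51.

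**Working correlation.** Section 6.2 does not name one. I repeated scenario A with an exchangeable structure and two visits, assuming that the first is seen for everyone and that mean and SD are the same at both. The excess falls to about 1 to 2 points. At correlation 0.8, for example, the ≥5% rates become 61.8% (comparator) and 92.5% (diet).

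**Limit of imputation.** If exactly the worst 20% at week 26 leave, the available ≥5% rates are 74.6% and 100%. Imputation from earlier loss (correlation 0.8) still gives 66.4% and 97.3%. It corrects only drop-out explained by weights already seen.

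**Scale against sampling error.** With 25 completers, the 95% half-width for a 59.7% rate is 1.96 × √(0.597 × 0.403/25) = 19 points. The standard error of the log odds ratio is √[1/(25 × 0.597 × 0.403) + 1/(25 × 0.907 × 0.093)] = 0.80. The scenario A shift is ln(7.72/6.54) = 0.17, about one fifth of that.

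**The case against.** The strongest objection is that the protocol never says the responder analysis uses observed weights only. A reader might infer this because imputation is repeated for the per-protocol analysis and not for the responders, but it is an inference from silence. Running the GEE on imputed data would be compatible with the text, and the SAP may say exactly that. This stands: there is no contradiction in the protocol, and confirmation in the SAP would settle the matter. It does not remove the point, because section 6.2 assigns missing-data handling analysis by analysis and fixes for the responders a method that, run as written, carries the stronger assumption.

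A reader might also infer that the responder results will be biased upward. The documents do not support that. Bias needs both an available-weights analysis and drop-out related to earlier loss. Even then it is the arm-level rates that rise, while the planned effect measure, the odds ratio, can go either way.

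It is also fair to say that the shifts are small against the sampling error, and that section 6.2 sets a significance level only for the primary analysis.

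Finally, reporting odds ratios alone is a legitimate choice. Under the section 6.1 assumptions, the chance that all of 25 diet-arm completers reach 5% is 0.907^25 ≈ 8.6%, and the odds ratio would then have no finite estimate. That is a contingency for one threshold in one arm at one visit, not an error in the plan.

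**Conclusion.** The point holds in a limited form. As written, the responder GEE is the one analysis of visit weights in section 6.2 that would generally need completely random drop-out; the imputed t-test and the mixed model need only missing-at-random. If poor early losers leave at about the planned rate, week-26 responder rates could be overstated by about 1 to 6 points, towards the lower end with an exchangeable working correlation. These figures rest on normality, the section 6.1 means and SDs, and assumed drop-out mechanisms and visit correlations. The primary result is not affected. The case for acting is consistency between analyses of the same weights, at little cost, rather than a large expected bias.

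**What to change.** State in section 6.2, or confirm in the SAP with a cross-reference, that:

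- weight loss is multiply imputed at every analysed visit (weeks 10, 16, 26 and 52) from arm and the weight loss at the other visits;
- 5% and 10% status is derived from the imputed weights after imputation;
- the logistic GEE is fitted to each imputed data set and the results are combined by Rubin's rules.

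A risk difference with its 95% confidence interval beside the odds ratio would be useful but is optional.

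The cost is modest but not nil. The imputation is described for the primary outcome at week 26, so it must be extended, in particular to week 52. The reported responder rates may be slightly less favourable. It would not cure drop-out that depends on weights never observed.

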Procedures/assessments	Phase 0: Screening and randomization		Phase 1: Lifestyle + NB with vs without VLCKD							Phase 2: Lifestyle + NB (all participants)				Follow-up (all participants)		
	Screening (In-clinic)	Randomization (in-clinic)	Remote	Remote	Remote	Remote	Remote	Remote	In-clinic (study specific)	Remote	Remote	In-clinic (Routine)	Remote	Remote	In-clinic (study specific)	In-clinic (routine)
Visit	V1	V2	V3	V4	V5	V6	V7	V8	V9	V10	V11	V12	V13	V14	V15	V16
Timing of visits (weeks)		Start	Start	W3	W4	W6	W8	W10	W10	W12	W16	W16	W20	W26	W26	W52
Visit window (days)									±30			±30			±30	±30
Lifestyle program			X		X		X			X	X		X	X		
Naltrexone/bupropion (NB)		X							X			X			X	X
VLCKD			(X) ¹	(X) ¹	(X) ¹	(X) ¹	(X) ¹	(X) ¹								
Screening assessments and randomization																
Informed consent	X ²															
Inclusion/exclusion criteria	X	X														
Randomization		X														
Anthropometric data (height, weight, waist circumference)		X							X			X			X	X

Clinical examination (Blood pressure, heart and lung auscultation, abdominal palpitation and percussion)		X							X			X				X	X
Laboratory tests																	
Fasting glucose		X							X			X				X	X
Hemoglobin A1c		X										X					X
Lipids: LDL-cholesterol, HDL-cholesterol, triglycerides		X							X			X				X	X
Liver test: AST, ALT, gamma-GT, alkaline phosphatase, total bilirubin, albumin		X										X					X
Kidney function: creatinine, eGFR		X										X					X
Thyroid function: TSH, free T4		X										X					X
Uric acid		X										X					X
Questionnaires																	
The PsyEndoAUDIT questionnaire ³		X							X			X				X	X
The PsyEndoCIDI questionnaire ³		X							X			X				X	X
The PsyEndoEDE questionnaire ³		X							X			X				X	X
The PsyEndoHADS questionnaire ³		X							X			X				X	X
Nederlandse vragenlijst voor eetgedrag ³		X							X			X				X	X
The ObesitasIPAQ questionnaire ³		X							X			X				X	X

The quality of life (SF-36) questionnaire ³		X							X				X			X	X
The outtake questionnaire															X		
Reason for discontinuation		X							X			X			X	X	
(Serious) Adverse event (S)(AE) assessment		X							X			X			X	X	

- Depending on randomization in either intervention (with VLCKD) or comparator group (without VLCKD).
- Informed Consent must be obtained prior to performing any other Trial-related procedures as part of the standard of care.
- See appendix 4 for the respective questionnaires.

I Background and Rationale

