4.5 By visit

There are five scheduled in-clinic visits, each involving a blood draw. Among these, three visits are routine for naltrexone/bupropion, which include the initial intake and visits after 16 and 52 weeks. The study-specific visits occur at 10 weeks and 26 weeks. During the routine visits, only fasting glucose and lipid levels (LDL-cholesterol, HDL-cholesterol, triglycerides) will be assessed in the blood. However, during the study-specific visits, in addition to fasting glucose and lipids, the following parameters will also be examined in the blood: Hemoglobin A1c, liver function (AST, ALT, gamma-GT, alkaline phosphatase, total bilirubin, albumin), kidney function (creatinine, eGFR), thyroid function (TSH, free T4), and uric acid. For a detailed overview of the visit schedule, please refer to the Study Flowchart.

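### Does measuring weight at only four follow-up visits make the planned Cox hazard ratio for time to 5% and 10% weight loss unsound?

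*Protocol*

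**What the plan says.** Section 2.3 of the protocol lists among the secondary endpoints "The time to reach a weight loss percentage of 5% and 10" per cent. Section 6.2 tests this endpoint with a log-rank test and adds: "Additionally, a Cox model will be used for the estimation of the hazard ratio with 95% confidence interval". The table in section 6.2.1 repeats the choice: "Log-rank test and Cox model for time-to-event data". Neither place names a tie method, a time scale (labelled visit or calendar date) or a continuous-time version of the model.

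In the Study Flowchart the row for height, weight and waist is marked at baseline and at weeks 10, 16, 26 and 52. Each of these follow-up visits has a window of ±30 days, and no weight is marked at the remote contacts. Section 4.5 agrees: "There are five scheduled in-clinic visits, each involving a blood draw".

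The opening of section 6 states that the detailed description of the analysis is in a trial-specific statistical analysis plan. Only the protocol is available here.

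**The concern.** A Cox model orders patients by the time of their event. In this trial that time is never observed: a patient who is below 5% at week 10 and above it at week 16 crossed somewhere in between. Analysed by visit label, all events fall on four times and the ties are heavy. Analysed by calendar date, the ±30-day windows let the week-10 visit of one patient fall later than the week-16 visit of another, so the order of events can be reversed.

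The hazard ratio with its interval is the effect estimate planned for this endpoint. If several analyses that all satisfy section 6.2 gave clearly different values, the result would depend on an unstated software option, in a trial that is not blinded. That makes the question worth checking.

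**Working it through.** **Inputs.** The protocol gives no hazard ratio or event rate for this endpoint, so there is no figure of its own to reproduce. Section 6.1 gives means and SDs of weight loss of 6.75% (7.12) in control and 12% (5.3) in the experimental arm, 20% drop-out and 31 patients per arm. Further assumptions are needed: these values are normal and refer to week 26, the share above the threshold at week 26 is the share that has crossed, and crossing times are exponential.

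**Implied hazard ratio.** The share that has crossed is p = 1 − Φ((threshold − mean)/SD), and under exponential times HR = ln(1 − pE)/ln(1 − pC).

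- 5%: pC = 1 − Φ((5 − 6.75)/7.12) = 0.5971; pE = 1 − Φ((5 − 12)/5.3) = 0.9067; HR = ln(0.0933)/ln(0.4029) = 2.61.
- 10%: pC = 0.3240; pE = 0.6470; HR = ln(0.3530)/ln(0.6760) = 2.66.

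**How heavy the ties are.** By week 10 at the 5% threshold, control reaches 1 − 0.4029^(10/26) = 0.295 and the experimental arm 1 − 0.0933^(10/26) = 0.598. Of 31 per arm that is about 9 and 19, so about 28 of 62 patients share one event time before drop-out.

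**What the tie method does in one table.** Take 31 per arm, no drop-out, and first crossings of 5% at the four visits of 12, 4, 3, 2 (control) and 23, 3, 2, 1 (experimental). The numbers at risk are then 31/31, 19/8, 15/5 and 12/3. The Breslow estimate θ solves Σ d·n₁θ/(n₀ + n₁θ) = 29, the number of experimental events. At θ = 1.91:

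35(1.91)/2.91 + 7(15.28)/34.28 + 5(9.55)/24.55 + 3(5.73)/17.73 = 22.97 + 3.12 + 1.94 + 0.97 = 29.0.

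Breslow keeps all 62 patients in the denominator for each of the 35 week-10 events, which pulls the estimate towards 1. Efron removes the tied patients step by step and gives 2.41 from the same counts. A grouped-time complementary log-log model gives 2.54.

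**Large-sample values.** Drop-out is 20% by week 26 at a constant rate, and visit dates are uniform within ±30 days.

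| Handling | 5% (true 2.61) | 10% (true 2.66) |
|---|---|---|
| Cox, labelled visit, Breslow ties | 1.99 (−24%) | 2.26 (−15%) |
| Cox, labelled visit, Efron ties | 2.47 (−5%) | 2.60 (−2%) |
| Cox, actual dates, Efron ties | 2.37 (−9%) | 2.44 (−8%) |
| Grouped-time complementary log-log | 2.58 (−1%) | 2.64 (−1%) |
| Discrete (conditional logistic) ties | 3.44 | 3.10 |

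The last row is on an odds-ratio scale. It answers a different question from the hazard ratio that section 6.2 asks for, so it should not count as movement of that hazard ratio.

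**At the trial's own size.** With 31 per arm and the same drop-out, 95% interval coverage at 5% is 94% for Efron by visit and 95% for the grouped-time model, with a simulation error of about 0.5 points. The root mean squared error of the log hazard ratio is 0.31 against 0.34 at 5%, and 0.35 against 0.37 at 10%, in Efron's favour. Efron's large-sample shift on the log scale is ln(2.61/2.47) = 0.055 and ln(2.66/2.60) = 0.023, small beside those errors. A separate simulation by labelled visit without date scatter gives:

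| Model | Median HR, 5% / 10% | Coverage | RMSE of log HR |
|---|---|---|---|
| Efron Cox | 2.51 / 2.65 | 96% / 96% | 0.31 / 0.36 |
| Complementary log-log | 2.75 / 2.75 | 94–95% | 0.35 / 0.38 |

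**Dates.** Week 10 spans days 70 ± 30 = 40–100 and week 16 spans days 112 ± 30 = 82–142, an overlap of 18 days. If the dates of two patients were independent and uniform over the whole window, a week-10/week-16 pair would be reversed with probability 18²/(2 × 60 × 60) = 4.5%. Visits clustered near their target day would give less. The protocol does not say that calendar dates will be used.

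**The case for a change.** The strongest case for a fault is that the protocol itself names the model, twice, next to a schedule that can only yield grouped times, and says nothing about the mismatch. The arithmetic supports part of this. Efron and Breslow differ by a median factor of 1.23 at 5% and 1.14 at 10% on the same simulated trials. Labelled visit against actual date (both Efron) differs by a median factor of 1.09 and 1.14, and by 1.25 and 1.35 at the 90th percentile. An analyst who accepted Breslow ties by visit would report a hazard ratio that is too small, with coverage at 5% of 92% with drop-out and 89% without. In an unblinded trial it is right that this choice be made before results are seen.

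What stands is that the choice matters and has to be written down. What does not follow is that the protocol is wrong. A Cox model for tied data is still a Cox model, and the Efron form by visit, or the grouped-data form of the proportional-hazards model, fits the words of section 6.2. The tie method and the event-date convention are ordinary content of a statistical analysis plan, and section 6 points to one. Replacing Cox by a complementary log-log model would be a preference: that model is closer in large samples but slightly more variable, and not clearly better, at 31 per arm.

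**Conclusion.** The concern does not hold. The visit schedule does group the event times, but the planned estimator can handle that within the protocol's wording, at a cost of about 5% (5% threshold) and 2% (10% threshold) in the large-sample hazard ratio and with coverage of about 95%. The wide spread appears only if one adds a Breslow choice the protocol does not make, or counts an odds ratio as a hazard ratio. What remains is detail on one secondary estimate that a protocol commonly leaves to the analysis plan.

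Nothing else depends on it. Both arms share one schedule, so the log-rank test is not in question. Section 6.2 also gives odds ratios per time point for the weight-loss proportions, which need no event time. The week-26 t-test and the 62 patients do not involve this endpoint.

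The sizes rest on the assumptions set out above, none of which the protocol states for this endpoint. If the diet effect were concentrated before week 10 (experimental hazard 5.2 and 5.3 times control until then, equal afterwards), no single true hazard ratio would exist. Cox on daily weights would then give 3.03 and 2.40, and Efron by visit 2.83 and 2.38, so Efron by visit would still stay near what daily weighing would have shown.
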